6.3.3.4 Neurologic Toxicity

Neurological toxicity has been observed in patients treated with oxaliplatin. This neurotoxicity has included paresthesias and dysesthesias of the hands, feet, and peri-oral region. Patients treated with oxaliplatin in this study will be counseled to avoid cold drinks and exposure to cold water or air, especially 3-5 days following oxaliplatin administration. Dose adjustments for neurological toxicity will be based on the following table.

	Duration of Toxicity		
Neurological Toxicity	≤7 days	>7 days	Persistent ^A

Paresthesias/dysesthesias ^B that do not interfere with function (Grade 1)	No change	No change	No change	
Paresthesias/dysesthesias ^B interfering with function, but not activities of daily living (ADL) (Grade 2)	No change	No change	Decrease dose by 50%	
Paresthesias/dysesthesias ^B With pain or with functional Impairment that also Interfere with ADL (Grade 3)	No change	Decrease dose by 50%	discontinue oxaliplatin	
Severe paresthesias/ dysesthesias ^B that are disabling or life- threatening (Grade 4)	Withdraw from study	Withdraw from study	discontinue oxaliplatin	
ACUTE (during or after the 2 hour infusion) laryngopharyngeal dysesthesias (also see below)	Increase duration of future infusions to 6 hours ^c	Increase duration of future infusions to 6 hours ^C	Increase duration of future infusions to 6 hours ^C	

^A Not resolved by the beginning of the next cycle

^B May be cold-induced

^c May also be pretreated with benzodiazepines

Note on laryngopharyngeal dysesthesia: a loss of sensation of breathing (acute respiratory distress) without any objective evidence of respiratory distress (hypoxia, layngospasm, or bronchospasm) has been observed. This neurotoxicity may be induced or exacerbated upon exposure to cold. Should a patient develop laryngopharyngeal dysesthesia, the patient's oxygen saturation will be evaluated via a pulse oximeter, and, if normal, an anxiolytic agent or benzodiazepine will be given and the patient should be observed in clinic until the episode has resolved. The infusion may be continued at 1/3 the rate. Because this syndrome may be associated with the rapidity of oxaliplatin infusion, subsequent doses of oxaliplatin should be administered as 6-hour infusions (instead of the normal 2-hour infusion).

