6.3.3.5 Dose Modifications for Other Non-Hematologic Toxicity

CTC Grade	Action	5-FU, % of	Oxaliplatin, % of		
		Previous Dose	Previous Dose		
1	Continue therapy	100	100		
2	Continue therapy	100	100		
3	Resume when	75 ^{1, 3}	75 ^{2, 3}		
	toxicity <= Grade 1				
4	Resume when	50 ^{1, 3}	50 ^{2, 3}		
	toxicity <= Grade 1				

¹See section 6.4.4 for dose reductions of 5-FU for Hand-Foot-Skin Reaction.
 ²No Dose reduction of Oxaliplatin for Grade 3 or 4 Hand-Foot-Skin Reaction.
 ³No dose reduction of 5-FU or Oxaliplatin need to be made for asymptomatic Grade 3 or 4 Amylase or Lipase elevation.

Pertains to treatment-related toxicity, not including diarrhea, nausea/vomiting, melena/hematemesis, neurologic toxicity (see above). Sorafenib dose should be adjusted as per the table in Section 6.4.1. For hematologic toxicity, see Section 6.3.2.

Doses of chemotherapy that have been reduced will not be re-escalated. Patients who do not recover to Grade 1 within 6 weeks will go off study.

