6.4.1 Dose Reduction Levels

The starting dose of sorafenib is 400 mg twice a day. Study medication will be administered daily on a continuous basis.

Doses will be delayed or reduced for clinically significant hematologic and nonhematologic toxicities that are related to protocol therapy according to the guidelines shown in the Dose Delays/Dose Modifications table that follows. Dose modifications will follow predefined dose levels: Dose adjustments for hematologic toxicity are based on the blood counts obtained in preparation for the day of treatment.

Dose modification levels for sorafenib							
Dose	Sorafenib						
Starting Dose	400 mg twice daily						
1 st Dose Reduction Level	400 mg once daily						
2 nd Dose Reduction Level	200 mg once daily						

Recommended Dose Modification of sorafenib for Hematologic Toxicities										
Toxicity	ANC(x 10 ⁹ /L)	Hemoglobin (g/dL)	Platelets (x 10 ⁹ /L)	Sorafenib						
Grade 1	<lln-1.5< td="">< LLN – 10.0	<lln-75< td="">Treat on time No change	</lln-75<>	</lln-1.5<>	< LLN – 10.0	<lln-75< td="">Treat on time No change	</lln-75<>	Treat on time No change						
Grade 2	≥ 1.0 to < 1.5	< 10.0 - 8.0	≥ 50 to < 75	Treat on time No change						
Grade 3	≥ 0.5 to < 1.0	< 8.0 - 6.5	≥ 25 to < 50	Treat on time Reduce by one dose level						
Grade 4	< 0.5	Life-threatening consequence; urgent intervention indicated	<25	Delay sorafenib until toxicity resolves to Grade 2 or less then Reduce by two dose levels ¹						
Febrile Neutropenia				Sorafenib held until toxicity has resolved to Grade 2 or less; when sorafenib is restarted, reduce by one dose level ²						

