6.4.3 Dose modification for non-hematologic toxicities¹

Recommended dose modification for non-hematologic toxicity (excluding hypertension and hand foot skin reaction, diarrhea and fatigue.									
Grade	Dose Interruption	Dose Modification							
• Grade 0-2	Treat on time	No Change							
• Grade 3	Interrupt until ≤Grade 2	DECREASE one dose level							
• Grade 4	OFF protocol therapy	OFF protocol therapy							
 If no recovery after 21 day delay, treatment will be discontinued unless subject is deriving clinical benefit 									

¹For sorafenib dose reductions for diarrhea, nausea, and vomiting, see sections 6.3.4.1 and 6.3.4.2.

For HFSR, sorafenib and 5-FU should be both reduced; For diarrhea, sorafenib, 5-FU and oxaliplatin should all be reduced; For fatigue, sorafenib, 5-FU and oxaliplatin should all be reduced.

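### The Grade 4 neurotoxicity row in Section 6.3.3.4 is internally inconsistent across its duration columns and, read with Section 6.4.3, leaves 5-FU/LV unsettled

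*Combined protocol and SAP*

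**What the plan says.** Section 6.3.3.4 states that "Dose adjustments for neurological toxicity will be based on the following table". The table crosses four severity grades with three duration columns: up to 7 days, more than 7 days, and Persistent. A footnote defines Persistent as "Not resolved by the beginning of the next cycle". Section 5.1.2 sets the cycle at 28 days.

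The fourth row covers severe symptoms "that are disabling or life- threatening (Grade 4"). Its first two cells read "Withdraw from study". Its third, Persistent, stops oxaliplatin and mentions no other drug.

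Three other provisions bear on the same event:

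- Section 6.4.3, under sorafenib dosing, sends Grade 4 non-hematologic toxicity "OFF protocol therapy". Its title limits it by "excluding hypertension and hand foot skin reaction, diarrhea and fatigue", and its footnote redirects diarrhea, nausea and vomiting. Neither names neurotoxicity.
- Section 6.4.1 applies the sorafenib rules to "hematologic and nonhematologic toxicities that are related to protocol therapy", so a toxicity caused by oxaliplatin is within reach.
- Section 6.3.3.5, the general chemotherapy table, does exclude neurotoxicity by name: "Pertains to treatment-related toxicity, not including diarrhea, nausea/vomiting, melena/hematemesis, neurologic toxicity (see above").

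**The concern.** Dose rules should not become more lenient as a severe toxicity lasts longer. Here a disabling or life-threatening neuropathy that clears within a week takes the patient out of the study, while one still present at the next cycle stops a single drug.

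Two things are at stake. The first is a clear instruction to the site for a serious toxicity, including what to do with the other drugs. The second is follow-up. Whether the patient leaves the study changes with the column, and the off-study date ends time to treatment failure (defined in Section 10.2, although not an objective in Section 1.0). If study withdrawal is taken literally, the 8-week scans behind the primary endpoint, time to progression (TTP), can also stop before progression.

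**Working it through.** The plan gives no figure on this point to reproduce. The check is a reading of the cells, then a rough count.

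**1. The table, in paraphrase (Section 6.3.3.4)**

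| Grade | ≤7 days | >7 days | Persistent |
|---|---|---|---|
| 1 | no change | no change | no change |
| 2 | no change | no change | halve dose |
| 3 | no change | halve dose | stop oxaliplatin |
| 4 | leave study | leave study | stop oxaliplatin |

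Grade 1 is flat and Grades 2 and 3 tighten from left to right. Only Grade 4 loosens. Its Persistent cell has the same action as the Grade 3 cell above it.

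**2. Ways to read the columns**

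- *Exclusive:* the longest-lasting Grade 4 event gets the mildest action.
- *Overlapping:* an event starting on Day d has lasted 29 − d days at the next Day 1. Onset on Day 15 gives 29 − 15 = 14 days, which is both more than 7 days (leave study) and Persistent (stop oxaliplatin). Onset on Day 25 gives 29 − 25 = 4 days, which is both up to 7 days and Persistent.
- *In time order:* every Grade 4 event first meets a withdrawal cell, so the Persistent cell is never used.

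No reading gives a coherent row in which all three cells have a use.

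**3. The other drugs in the Persistent cell**

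- Oxaliplatin: stopped by Section 6.3.3.4.
- Sorafenib: not mentioned in Section 6.3.3.4. Section 6.4.3 stops it, because neurotoxicity is not among the exclusions.
- 5-FU/LV: not mentioned in the cell. It stops if the Section 6.4.3 action means all protocol therapy. Its status is unstated if that action covers sorafenib only.

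**4. How many patients**

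Inputs: 40 patients (Section 14.1), and Grade 3-4 persistent neuropathy of 6% with oxaliplatin plus 5-FU/LV in second-line colorectal cancer (Section 6.2). The documents give no separate Grade 4 rate, so the Grade 4 share s is an assumption.

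- Expected Grade 4 persistent cases = 40 × 0.06 × s
- P(at least one) = 1 − (1 − 0.06 × s)^40

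| s | Expected | P(at least one) |
|---|---|---|
| 10% | 40 × 0.006 = 0.24 | 1 − 0.994^40 = 0.21 |
| 25% | 40 × 0.015 = 0.60 | 1 − 0.985^40 = 0.45 |

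Over all possible shares (0 to 1) the expected count runs from 0 to 40 × 0.06 = 2.4. The 7% overall Grade 3-4 rate in Section 6.2 is the wrong base for the Persistent cell, because it is not limited to persistent neuropathy.

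**The case against.** The strongest defence is to read each section for its own drugs. Section 6.3 governs 5-FU and oxaliplatin, and Section 6.4 governs sorafenib. Where Section 6.3.3 means to direct sorafenib it says so, as for diarrhea, nausea/vomiting, and melena/hematemesis. On this reading, persistent Grade 4 neurotoxicity stops oxaliplatin under one section and sorafenib under the other, and the two rules are compatible. This largely stands. It does not repair the inverted row, and it leaves 5-FU/LV to inference.

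A reader might infer that Section 6.3.3.4 tells the site to continue sorafenib and 5-FU/LV, and so count three conflicting instructions with the three-week sorafenib rule that closes Section 6.4. The documents do not support that. The Persistent cell is silent on those drugs; it does not order them continued. Section 6.4.3 stops sorafenib for Grade 4 with no waiting period, so the three-week limit is largely moot. Its clause on FOLFOX is a conditional permission. Nor does Section 6.0 contradict the row: its allowance to stay on study with one component is general, and a specific row can narrow it.

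It is also fair that, applied in time order, the milder cell is never used. The flaw then has no practical effect, but the plan does not state that order.

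Finally, Section 10.2 asks for tumor documentation after therapy stops, Section 5.2.3 has an end-of-treatment reassessment, and the calendar has a six-monthly note. These help, but none requires 8-week scans until progression.

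**Conclusion.** The point holds as a minor inconsistency. The Grade 4 row loosens with duration, assigns two actions to one event, or contains an unused cell, depending on how the columns are read, and nothing elsewhere settles which. With Section 6.4.3, the treatment left unresolved is 5-FU/LV.

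The likely reach is 0.24-0.60 patients of 40, with a 21-45% chance of at least one. This rests on a colorectal cancer rate and an assumed 10-25% Grade 4 share. The true number may be zero: Section 2.4 reports less Grade 3-4 neuropathy with sorafenib than with placebo added to FOLFOX, and the reductions for lower grades act first.

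A reader might also infer repeat exposure to oxaliplatin, a biased TTP estimate or lost power. The documents show none of these. Every reading of the row stops oxaliplatin, no bias has been measured, and the Section 14 design is unaffected.

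**What to change.** Use one Grade 4 action in all three columns, consistent with Section 6.4.3: permanently discontinue oxaliplatin and stop sorafenib, with an explicit statement on whether 5-FU/LV stops or may continue. If the investigators want sorafenib to remain possible, add neurotoxicity to the Section 6.4.3 exclusions; the three-week rule then becomes relevant, and the text should say whether it applies. Setting all three cells to oxaliplatin alone, with no change elsewhere, would move the first two away from Section 6.4.3.

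Replace study withdrawal with discontinuation of protocol treatment, naming the drugs. Add one sentence that patients who stop for toxicity without progression keep the 8-week scans until progression, so that TTP is still observed.

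The cost is one clinical decision, a table row with matching wording, an amendment approved by the IRB (Section 13.1), and continued scans for a few patients. Sample size and analysis do not change.

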5.0 STUDY DESIGN

- 5.1Treatment Plan
- 5.1.1 Single arm, open label, phase II study
- 5.1.2Dosing schedule

Treatment will be administered on an outpatient basis. Expected adverse events and appropriate dose modifications for sorafenib, 5-FU, oxaliplatin are as described in Section 6.0. No investigational or commercial agents of therapies other than those described below may be administered with the intent to treat the patient's malignancy.

Patients will be treated as below:

Register:

Sorafenib 400 mg bid \rightarrow	Sorafenib 400 mg bid	\rightarrow	continue treatment
First two weeks	modified folfox, days 1, 15	5	until PD or intolerable toxiity

Every 28 days/cycle

For first two weeks, sorafenib will be given alone.

Cycle 1 and beyond:

Sorafenib 400 mg bid + modified FOLFOX (Oxaliplatin 85 mg/m2 followed by leucovorin 200 mg/m², followed by infusional 5-FU at 1200 mg/m²/d on Days 1 and 2 (2400 mg/m² total over 46 hours) repeated every 14 days for each cycle.

Oxaliplatin will be delivered at 85 mg/m²as a 2-hour infusion on day 1 and day 15 of every cycle.

Drugs 5-FU/LV		Oxaliplatin	Sorafenib
Treatment dates	Days 1,15	Days 1,15	Daily (days 1-28)
Dosage	LV: 200 mg/m2 5-FUCI: 2400 mg/m ² total (1200mg/m ² /d on day 1 and 2)	85 mg/m2	400 mg bid

Lead-in sorafenib alone treatment: first 2 weeks.

Each cycle is defined as 28-day treatments.

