6.0 DOSE MODIFICATION / TOXICITY MANAGEMENT

Study drug treatment will be modified in the event of certain adverse events, as shown in the tables below.

- Regardless of the reason for holding study drug treatment, the maximum allowable length of treatment interruption of FOLFOX is 6 weeks (the holding of 3 consecutive doses) and of Sorafenib is 3 weeks. If the patient needs to stop FOLFOX due to toxicity, they can stay on study as long as they continue with Sorafenib. If the patient needs to stop Sorafenib due to toxicity, they can stay on the study as long as they continue FOLFOX. If they need to stop both FOLFOX and Sorafenib for longer than the above time limits, they must be taken off the study and the Principle Investigator must be notified.
- Doses of chemotherapy that have been reduced will not be re-escalated.
- No held doses of Sorafenib or FOLFOX will be made up. If a patient misses a dose for toxicity, the patient will proceed to the next treatment day or cycle as scheduled.

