6.3 Dose Modification of 5-FU and Oxaliplatin

6.3.1 Toxicity will be evaluated weekly during the sorafenib lead-in period, weekly during the first 3 weeks of cycle 1 of FOLFOX-Sorafenib, and then once every two weeks for subsequent cycles. Dose modifications based on significant weight changes can be made in accordance to institutional practice.

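### Persistent neurotoxicity is defined by the next 28-day cycle although oxaliplatin is given every 14 days, so the Grade 2 reduction and the Grade 3 stop cannot be triggered at a Day 15 dose

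*Combined protocol and SAP*

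**What the plan says.** Section 6.3.3.4 sets oxaliplatin dose changes by grade and by three duration columns: up to 7 days, more than 7 days, and Persistent. Footnote A defines the third column as "Not resolved by the beginning of the next cycle".

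- Grade 2: no change in the first two columns; the dose is halved if Persistent.
- Grade 3: no change up to 7 days; halved beyond 7 days; oxaliplatin discontinued if Persistent.

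Section 5.1.2 states "Each cycle is defined as 28-day treatments" and gives oxaliplatin at 85 mg/m2 as a "2-hour infusion on day 1 and day 15 of every cycle". Section 6.0 says that after a missed dose "the patient will proceed to the next treatment day or cycle as scheduled", which treats a treatment day and a cycle as different things.

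The general table in section 6.3.3.5, which withholds treatment for Grade 3 toxicity until recovery, is expressly "not including diarrhea, nausea/vomiting, melena/hematemesis, neurologic toxicity (see above". Reduced chemotherapy doses are not raised again (section 6.0).

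**The concern.** Only the Persistent column reduces the dose for Grade 2 or stops oxaliplatin for Grade 3. Each cycle holds two doses, and only the Day 1 dose coincides with the start of a cycle. Two patients with the same grade, onset and duration of neurotoxicity, each seen 14 days after the last dose, therefore receive different instructions solely because one had just had a Day 1 dose and the other a Day 15 dose.

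What is at stake is cumulative oxaliplatin exposure in patients with unresolved neuropathy, and uniform dosing across patients. Section 5.1.2 sets no maximum number of oxaliplatin cycles, so this table is the main written control on neurotoxicity.

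**Working it through.** **Inputs**

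- Starting dose 85 mg/m2; doses 14 days apart on Days 1 and 15; cycle 28 days (section 5.1.2). The next cycle starts on Day 29.
- Table actions and footnote A (section 6.3.3.4).
- No re-escalation (section 6.0).

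**Conventions.** Toxicity that ends on a dose day counts as unresolved that day. Where toxicity is both longer than 7 days and Persistent, Persistent governs; otherwise that column would have almost no use.

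**Step 1: which episodes are compared.** At the next dose, an episode that began k days after the previous dose has been present 14 − k days. This exceeds 7 when k is 0 to 6. Such an episode falls beyond 7 days whether the column header means time elapsed so far or total length, so these figures do not depend on that reading.

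**Step 2: the dose at the next visit, as written.** Half of the starting dose is 0.5 × 85 = 42.5 mg/m2.

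| Present >7 days, unresolved at next dose | After a Day 1 dose (next dose Day 15, mid-cycle) | After a Day 15 dose (next dose Day 1, new cycle) | Difference |
|---|---|---|---|
| Grade 2 | 85 | 42.5 | 42.5 mg/m2 |
| Grade 3 | 42.5 | 0 (stopped) | 42.5 mg/m2 |

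**Step 3: the next two doses.** Onset is on the day of the dose and the starting dose is 85 mg/m2.

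| Episode | After Day 1, as written | After Day 15, as written | Either, with footnote A tied to the next dose |
|---|---|---|---|
| Grade 2, 20 days | 85, 85 | 42.5, 42.5 | 42.5, 42.5 |
| Grade 2, 28 days | 85, 42.5 | 42.5, 42.5 | 42.5, 42.5 |
| Grade 3, 20 days | 42.5, 42.5 | 0, 0 | 0, 0 |
| Grade 3, 28 days | 42.5, 0 | 0, 0 | 0, 0 |

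After a Day 1 dose, toxicity that lasts to Day 29 brings the Grade 2 reduction or the Grade 3 stop one dose later than after a Day 15 dose. If it clears between Day 15 and Day 29, that action does not apply at all. Toxicity resolved before the next dose is treated alike in both positions.

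**Step 4: does another rule act at Day 15?** Section 6.3.3.5 excludes neurologic toxicity. Section 6.3.2 does check blood counts before every dose, but only for hematologic toxicity. Sections 5.1.6 and 6.5 allow stopping for unacceptable adverse events or on the investigator's judgment; they set no rule for neuropathy.

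**Step 5: how many patients.** The only rates by severity are in section 6.2, for oxaliplatin with 5-FU/LV in second-line colorectal cancer: Grade 3–4 neuropathy 7%, all grades 73%. Carrying the 7% over to this trial is an assumption (different disease, no sorafenib). It gives 0.07 × 40 = 2.8, or about 3 patients with Grade 3–4 neuropathy at any time. Only the Grade 3 cases that arise after a Day 1 dose and are unresolved at Day 15 matter here. Grade 2 is not separated from Grade 1, so that part cannot be sized.

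**The case against.** The table can be read as a deliberate graduated rule. With a 28-day cycle all three columns have a meaning, and nothing in the protocol says the Persistent step was meant to act at every dose. On that reading, toxicity that clears before Day 29 is simply not Persistent, and no action has been missed. This stands as far as intent goes: a reader might infer a drafting error for the next dose, but the documents do not establish one. The objection does not explain why the same toxicity is handled more strictly after a Day 15 dose.

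The existing rule also softens the effect. Grade 3 toxicity beyond 7 days is already halved at Day 15 and stays halved, and investigators may stop treatment on judgment. Continuing full doses at Grade 2 matches the general approach in section 6.3.3.5. All of this is correct and limits the size of the problem. But discretion does not correct a written instruction of no change, and section 6.3.3.4 itself departs from the general Grade 2 approach once toxicity is Persistent.

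A reader might go further and infer that Grade 3 toxicity a few days old gets 85 mg/m2 at Day 15 against a permanent stop at Day 1. The documents do not support that contrast. It needs the duration header to mean time elapsed so far, and it needs Persistent to override the column for up to 7 days. The table states neither. The overlap of those two columns is a separate ambiguity.

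**Conclusion.** The point holds as a matter of safety and consistent dosing. For Grade 2 or 3 neurotoxicity present more than 7 days and unresolved at the next dose, the position in the cycle alone changes that dose by 42.5 mg/m2 from an 85 mg/m2 start. For Grade 3 it decides between a half dose and stopping oxaliplatin.

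This rests on taking the cycle as 28 days, as section 5.1.2 defines it, and on Persistent taking precedence over the column for more than 7 days. The Grade 1 and Grade 4 rows are outside the point. The number affected is probably small, going by the borrowed Grade 3–4 rate, but the documents do not allow it to be sized.

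A reader might also infer bias in the trial's results. The documents give no ground for that. Section 14.2.2 plans no analysis of dose reductions, and the power statement and time-to-progression test in section 14.2.1 do not depend on this rule.

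**What to change.** Change footnote A to: *Not resolved by the next scheduled oxaliplatin dose (Day 1 or Day 15)*. The instruction then no longer depends on where in the cycle the toxicity began. If Day 29 was intended, the sponsor should say so and explain why the two doses are treated differently.

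**Cost.** A one-line amendment, with the IRB approval that section 13.1 requires. No visits are added: toxicity is assessed weekly early on "and then once every two weeks for subsequent cycles" (section 6.3.1), and the study calendar places an assessment at each dosing visit.

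**Downside.** At Day 15, unresolved Grade 2 present more than 7 days goes from 85 to 42.5 mg/m2, and unresolved Grade 3 present more than 7 days goes from 42.5 mg/m2 to discontinuation. Some of these patients would have recovered by Day 29. The stricter action is the one the protocol already applies after a Day 15 dose.

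**Left to the sponsor.** Toxicity present 7 days or less and unresolved at a Day 1 already fits two columns. With the new footnote the same overlap arises at Day 15, so it is sensible to settle it in the same amendment. Whether by an order of precedence or by a held dose is a dosing decision that the documents do not determine.
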